Clear and refutable hypotheses of the R61 are: H1a) UE or UE&CIT will lead to significantly greater gains in CS than will ACCT and/or H1b) CIT or UE&CIT will produce significantly greater improvements in PO compared to ACCT. The **Go Signal** for continuing to the R33 will be a differential improvement, with an effect size of at least d=0.4, favoring UE or UE&CIT compared to ACCT on the psychophysical and/or electrophysiological CS task, *and/or* CIT or UE&CIT compared to ACCT on the JOVI and/or Ebbinghaus task. If a "go" signal is obtained, results of the R61 will be used to identify the most effective and efficient treatment (UE, CIT, or UE&CIT), and duration/dose, for use in the R33.

**Clear and refutable hypotheses of the R33 are:** H1) The optimal treatment identified in the R61 (e.g., UE&CIT) will be more effective than the control treatment (ACCT) in improving CS or PO in a new and larger sample; and H2) Improvements in target function will be related to changes on visual cognitive (i.e., visual learning and memory, reading), social cognitive (i.e., facial emotion recognition) and functional capacity measures. If the hypotheses in the R33 are confirmed, the results will inform the design of a later RCT to assess the efficacy of a visual remediation treatment for schizophrenia on a wider range of outcome variables. Instructions for the R33 state that it "should not be powered as strong tests of clinical efficacy but rather should test the link between... target engagement and functional outcome." Therefore, while we expect the correlations for R33 Aim 2 to be statistically significant, we do not hypothesize what the effect sizes will be. However, we would power a subsequent study based on the observed effect sizes in the R33.

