Milestones (Go/No-Go Criterion): We will proceed to the R33 phase if: 1) the UE-related effect size (i.e., the effect size of the difference between the UE&ACCT (or UE&CIT) and ACCT&ACCT groups in the degree of change in CS) is greater than or equal to Cohen's d=0.4 for **either** the psychophysical **or** ssVEP CS task: and/or 2) the CIT-related effect size (i.e., the effect size of the difference between CIT&ACCT (or UE&CIT) and ACCT&ACCT groups in the change on **either** of the PO tasks) is greater than or equal to d=0.4. Pre-post change scores for CS and PO target assessments will be calculated for each individual and used to determine effect sizes between groups. We will not control for baseline values consistent with recommendations to use "straight" change scores when examining cognitive change across two time points.

Rationale for our effect size choice: The effect size criterion we have chosen for the R61 "go" signal (d=0.4)

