is similar to that observed in many studies of cognitive remediation, and of other treatments for this population, such as skills training and family psycho-education. However, less is known about effect sizes of perceptual remediation, and most of the evidence on this in schizophrenia comes from studies of auditory remediation using the Posit Science auditory training module, which includes training on both low-level auditory targets and higher-level auditory-verbal cognition (e.g., verbal working memory and learning). Results from one study indicated an improvement in the target of auditory-processing speed that was of large effect (d=0.875). The authors also observed a medium-large effect on global cognition (d=0.73). Results from other studies of this auditory training module in schizophrenia have indicated large treatment effects (d=0.86) for both verbal learning and global cognition, and a medium effect (d=~0.65) on the auditory target of P50 gating. While these effect sizes are larger than our chosen criterion (d=.4), it is also important to note that some studies of Posit Science modules have not demonstrated significant improvement on non-trained tasks. Moreover, across studies, the largest effects have tended to come from studies where daily training (5 days a week) was used, and subjects were paid for completing training sessions, and these are two conditions that can rarely be met in real world psychiatric clinics. These considerations have informed our choice of the 'go signal' criterion (i.e., d=.4), because there are as of yet very few published studies of visual remediation in schizophrenia. One small (N=9) uncontrolled study of visual backward masking training found an effect size of d=.43 for improvement in the MATRICS domain of Visual Learning. Within our group, [name] observed an improvement in contour integration performance among participants with schizophrenia after 4 consecutive days of practice on a contour integration task (phi=0.63, which corresponds to a large effect). Even larger effect sizes were seen for changes in CS (d=0.96), and PO (d=0.85) in our small pilot sample of patients with schizophrenia (Section D1), but given the small sample size and lack of a control group in that study it can be assumed that the real effect size is lower. Thus, findings from these initial evaluations of visual remediation support our use of d=0.4 as a conservative level of change on the outcome measures and as a "go" signal for target engagement. However, we acknowledge that it is not yet clear from the literature how an effect of this size relates to meaningful improvements in visual and higher-order cognitive processing, and/or functional capacity. The proposed R33 will allow us to address this guestion in a preliminary manner. If results from this trial are positive, we will seek funding for a larger trial to evaluate the impact of this treatment on functional outcomes, and to identify mediators/moderators of treatment response. If the Go criterion is met for any of the treatment conditions, we will perform a thorough investigation of the effects of UE, CIT, and UE&CIT on the CS and PO target scores to determine which remediation strategy to use for the R33. Analyses will also include (i) assessment of the trajectory of performance on the target measures over the course of treatment; (ii) determinations of whether the improvements plateau prior to the 40th session or whether they continue throughout the training period; and (iii) evaluations of whether any combined effects of UE and CIT are additive or multiplicative. These goals will be accomplished by first graphically examining the trajectories of target change to assess whether they are linear, monotonic non-linear, guadratic, or any other shape. After that, appropriate models for longitudinal data analysis will be applied to estimate improvement rate and time to asymptote. We will account for CPZ-equivalent dose of antipsychotic medications in all models, using CPZ dose as a time-varying covariate if necessary, and will also account for type of antipsychotic medication and anticholinergic load. Those models will also be used to examine whether baseline characteristics moderate the effect of UE and/or CIT on the targets. These analyses will allow us to ascertain: 1) whether UE alone, by targeting CS function, has a cascading effect on PO; 2) whether CIT improves CS while targeting PO function; and 3) whether UE&CIT has a stronger effect than either intervention alone for any outcome. Based on these results, the optimal intervention will be determined based on it having a significantly larger effect size for at least one target. If all 3 treatment conditions are effective to an equivalent degree, the criterion will be reaching asymptotic level of improvement earliest.

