# Sample size determination:

The sample size of the R61 study (n=20/group) was selected to ensure that when the true size of the effect of UE or UE&CIT on the CS target, or CIT or UE&CIT on the PO target, is d=0.4, the 95% confidence interval (CI) for the effect size does not contain zero. Given data on the CS measure over time in the UE pilot study described earlier, a 95% confidence interval for an effect size of magnitude 0.4 is between .02 and .91. Since the observed effect size in that pilot data was actually much larger, 0.96, we are confident that we will be adequately powered to detect a meaningful effect. Since patients also improved on a measure of contour integration (d=0.85) in the pilot study, even though training was focused only on CS (our low-level visual target), setting the effect size at d=0.4 for both CS and PO seems reasonable. Note that although contour integration improved without PO training in the pilot study, this was unlikely due to practice effects on the test alone since two prior large studies did not find practice effects on the JOVI, in either healthy controls or

patients, over two or three repeated presentations separated by days or weeks, and a third study found improvements only with daily exposure to two versions of the task, and this did not occur for the schizophrenia group until the third day. Subjects who do not complete all 40 sessions of training will be invited to complete a "post-treatment" assessment after their last session; for non-completers who decline to participate in a post-treatment evaluation, the last post-baseline assessment will be used, unless the participant dropped out before the 10th session (the time of 1st post-baseline assessment), in which case his/her data will be not be used in the analyses. In such cases, we will recruit additional participants to reach the target sample size. We expect minimal dropout since most participants will be long-stay inpatients or partial hospital patients who are present on a nearly daily basis. For any dropout that does occur, we expect rates to be uniform across conditions, given that we have designed all conditions, including the active control, to be similarly engaging. Sufficient patients are available at both sites to recruit new subjects to replace any who discontinue. D.4 R33 Phase

[figure not shown]

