Aims: (i) To replicate and extend R61 results supporting initial visual target engagement using the optimal R61 treatment, in a new and larger sample; and (ii) to determine if visual target engagement is associated with improvements in specific cognitive (i.e., visual working memory, visual learning and memory, reading) and social cognitive (*i.e.*, facial emotion recognition) outcomes, as well as with changes in functional capacity. Study design: The R33 will be a two parallel-arm RCT comparing the optimal R61 treatment to the control (ACCT) treatment. 100 subjects will be enrolled over 3 years, 50 from NKI and 50 from Rutgers. Visual and clinical outcome assessments will be conducted at baseline, and at intervals determined based on R61 results, including a 6-month follow-up (with attrition considerations and procedures identical to the R61 (see D.3). **Randomization:** Subjects will be randomly assigned, within site, to the optimal or control treatment in a ratio of 1:1. Treatment assignment for eligible subjects will occur after completion of baseline testing, to avoid bias. Assessments: Visual Targets and Cognitive, Social Cognitive, and Functional Capacity. No matter which intervention is used for the R33, visual tests will include both tests of CS, and both tests of PO used in the R61. See below (section D.6.c) for descriptions of the cognitive, social cognitive, and functional capacity measures. **Data analysis:** An intention to treat approach to data analysis will be used in this clinical trial. For all analyses. statistical significance will be defined as p < 0.05, unless specified otherwise. Bonferroni corrections will be applied to multiple testing, as appropriate. H1: The optimal R61 treatment will be more effective than the control treatment (ACCT) in improving CS and/or PO test scores (to be determined based on the R61 outcome). This will be tested using a linear mixed effects model in which the values of the target(s) at each time point are modeled as a function of treatment group (experimental, control), time, time x group, and potential moderators and mediators (e.g., age). We will use Akaike's Information Criterion (AIC) as the deciding metric to determine the optimal model to account for within-subject correlations between repeated measures (e.g., autoregressive of order 1, AR(1), which assumes stronger within-person correlation for measurements closer in time, or other structures). If the time x group interaction is significant, we will use model-based estimation procedures to estimate the magnitude of the effect. We will also explore differential effects of the treatment on CS vs. PO. H2: Improvements in visual processing, as observed in CS and/or PO (based on R61 results), will be related to changes on specific cognitive (i.e., visual working memory, visual learning and memory, reading), social cognitive (i.e., emotion recognition), and functional capacity measures. We will assess correlations between visual target scores and cognition, social cognition, and functional capacity, and also evaluate whether changes in the target(s) either mediate or moderate treatment effects on these outcomes. An approach and computational tool described by Hayes will be used to model any mediation and /or moderation effects, including indirect effects in models that involve mediation. Sample size determination: The sample size for the RCT in the R33 phase was selected to ensure sufficient power to detect medium effects of the experimental intervention on the target(s). For Aim 1 of the R33, 50 subjects per condition allows 80% power for a 2-tailed test with  $\alpha$ =0.05 to detect d=0.57. For Aim 2, with n=50 in the active perceptual training group, correlations of at least r=0.38 between changes in performance on target measures (CS and/or PO) and changes in cognitive, social cognitive, and functional capacity can be detected with 80% power using a 2-tailed test with  $\alpha$ =0.05. Also, for Aim 2, n=50 (i.e., active perceptual intervention only) allows for detecting a correlation of r=0.43 when making a strict Bonferroni adjustment for 3 outcomes (2-tailed  $\alpha$ =0.017), and r=0.51 when correcting for 15 outcomes (2-tailed  $\alpha$ =0.003). In accordance with instructions that the R33 "should not be powered as a strong test of clinical efficacy...", our focus on effect size is exploratory and not confirmatory. We will use our observed effect sizes to power a later RCT. D.5 Interventions

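### The R61 sample-size justification is wrong as written: with 20 per arm the 95% CI around d = 0.4 runs from about -0.23 to 1.02, so it does not exclude zero

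*Combined protocol and SAP*

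**What the plan says.** Section D.3, Sample size determination, says that 20 per group was chosen so that when the true effect "is d=0.4, the 95% confidence interval (CI) for the effect size does not contain zero". Citing the UE pilot study's CS data over time, it then states that "a 95% confidence interval for an effect size of magnitude 0.4 is between .02 and .91". Because the pilot effect was larger (0.96), it adds: "we are confident that we will be adequately powered to detect a meaningful effect".

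The Milestones paragraph of D.3 defines the effect size. Individual pre-post change scores are "used to determine effect sizes between groups", each active arm is set against ACCT&ACCT, and baseline is not controlled for. The study design paragraph gives 20 per arm.

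Two other R61 statements depend on statistical significance. H1a in section B predicts that "UE or UE&CIT will lead to significantly greater gains in" CS than the control, and H1b says the same for PO. Section D.3 also says that "the optimal intervention will be determined based on it having a significantly larger effect size for at least one target".

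**The concern.** The stated interval is too narrow for 20 v 20, and it is not centred on 0.4: its midpoint is (0.02 + 0.91)/2 = 0.465. It is the only quantitative basis given for the R61 size. If it is wrong, the phase has much less precision than the plan promises, and a non-significant result at an observed d of 0.4 would look surprising when it is certain.

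The supporting sentence about power is also weak. In D.1, the 0.96 stands beside the shift in peak spatial frequency (3.14 to 4.15 cycles/degree, p = .14) in six uncontrolled patients. The CS target in D.6.b is mean sensitivity at 0.5 and 1 cycle/degree. Section D.3 itself says of the pilot effects that "it can be assumed that the real effect size is lower".

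**Working it through.** **Inputs.** n = 20 per arm and d = 0.4 (D.3); two-group contrast of change scores without baseline adjustment (D.3, Milestones); 95% two-sided interval. Early dropouts are replaced, so n stays at 20. Test-retest ICCs of .76 (0.5 cpd) and .67 (1 cpd) come from D.6.b.

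**Check of method against the plan's R33 figure.** Section D.4 says that "50 subjects per condition allows 80% power for a 2-tailed test" at d = 0.57. The two-sample t-test with n = 50 per arm gives 80% power at d = 0.566, so that figure is reproduced.

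**R61 interval at d = 0.4, 20 v 20.**
- SE = sqrt(1/20 + 1/20 + 0.4²/(2 × 40)) = sqrt(0.100 + 0.002) = 0.319.
- Wald CI: 0.4 ± 1.96 × 0.319 = -0.23 to 1.03.
- Exact CI (inverting the noncentral t, 38 df): -0.23 to 1.02.
- Smallest observed d that excludes zero: t(.975, 38) × sqrt(2/20) = 2.024 × 0.316 = 0.64.
- Two-sided power at true d = 0.4: 23%.
- True d for 80% power: 0.91.
- An observed 0.4 excludes zero only from about 50 per group. Power of 80% at a true 0.4 needs about 100 per group.

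**Attempts to reproduce .02 to .91.**

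| Variant (95%) | Interval |
|---|---|
| 20 v 20, d = 0.4, change-score SD | -0.23 to 1.02 |
| 40 v 20, d = 0.4 | -0.14 to 0.94 |
| 40 v 40, d = 0.4 | -0.04 to 0.84 |
| One sample, n = 20, d = 0.4 | -0.06 to 0.85 |
| 20 v 20, baseline-SD scale, r = .67 | -0.12 to 0.92 |
| 20 v 20, baseline-SD scale, r = .76 | -0.04 to 0.84 |
| 20 v 20, baseline-SD scale, assumed r = .80 | 0.00 to 0.80 (lower limit -0.005) |
| 20 v 20, baseline-SD scale, assumed r = .83 | 0.03 to 0.77 |
| 40 v 40, d = 0.465 | 0.02 to 0.91 |

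On the baseline-SD scale, SE = sqrt(2(1 - r) × 2/20), with the SD treated as known and t = 2.024. Only the last row gives both limits, and it uses neither the stated effect nor the stated group size. It is a numerical match, not evidence of how the figure was made.

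**Consequences for R61.**
- Go rule: at a true d of 0.4, one comparison reaches an observed d of at least 0.4 about 50% of the time. The 23% is therefore not the chance of a Go.
- H1a: there are four comparisons (two arms, two CS tasks) with a shared control. If every true effect is 0.4, success means two-sided p < .05 in the right direction without correction, and the two tasks correlate at .41, the chance of at least one success is about 53% by simulation. For assumed correlations of .7 to .3 it is 48% to 55%.
- Choice of the R33 treatment: two 20-patient arms that truly differ by 0.4 would be separated about 23% of the time on change scores.

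**The case against.** The strongest reply is that the plan does not name the SD used to standardise d, and that it ties its interval to pilot data that are not shown. If d is scaled by the baseline SD and pre-post correlation is high, the interval narrows. The two ICCs are for single frequencies, and their average is more reliable. With an assumed correlation c between the two frequencies (and independent errors), reliability is (.76 + .67 + 2c)/(2 + 2c), which is .78 at c = .3 and .83 at c = .7. That spans the point, about .80, where zero drops out. If the baseline SD is estimated from the control arm and r is assumed to be .81, simulated values of d fall mostly between 0.02 and 0.88, which is close to the printed range.

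This shows that the origin of the figure cannot be settled from the documents. It does not rescue the claim. The simulated range is a sampling range around a known true value, not a CI, and its upper end still falls short of .91. Even if an observed 0.4 only just excluded zero, a true 0.4 would do so in only about half of trials, so 20 per group would not guarantee it. Matching the R33 power figure likewise says nothing about how the R61 interval was derived.

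Other points stand as limits. The Go rule does not use the interval. The choice of R33 treatment is to draw on longitudinal models, which may be more precise than a change-score test by an amount that cannot be computed here, and it has a fallback based on time to asymptote. R33 is a replication in a new sample. The .41 is a correlation between the two CS indices, not stated to be one between change scores, and two-sided .05 is written only for R33, so the 53% is indicative.

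**Conclusion.** The concern holds. For the contrast that D.3 defines, the CI around d = 0.4 with 20 per arm is about -0.23 to 1.02, not .02 to .91, and the stated reason for n = 20 fails. The claim of adequate power fails as well: 80% power needs a true d of about 0.91, and the 0.96 offered in support is an uncontrolled estimate from six patients that D.1 prints beside a different measure from the target.

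The main figures assume standardisation by the change-score SD and a two-sided 5% level. On the baseline-SD scale with the documents' own ICCs, zero still lies inside the interval. It is excluded only with an assumed correlation of about .80 or more, and the guarantee fails even then. The error must be corrected because this is the sole stated basis for the R61 size, but it does not undermine the Go rule itself.

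**What to change.** Keep 20 per arm. In D.3, Sample size determination, replace the interval and the reason given for n with text such as:

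> With 20 per arm the 95% CI for an observed d of 0.4 is about -0.23 to 1.02. Power for a single comparison at a true d of 0.4 is about 23%, and an observed d of about 0.64 is needed to exclude zero.

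Then:
- Delete the statement that the phase is adequately powered.
- Label 0.96 as the effect on peak spatial frequency, or give the pilot effect on the low-spatial-frequency target.
- Describe R61 as an estimation and go/no-go phase, and report every Go effect size with its 95% CI.
- Beside the rule for choosing the R33 treatment, note that a change-score comparison of two 20-patient arms needs an observed difference of about 0.64 to be significant, and that the longitudinal model may differ.
- If the sponsor holds a derivation of .02 to .91, print its standardiser, assumed correlation and formula. The claim that 20 per group ensures exclusion of zero should still go.

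The cost is wording only: no more patients and no change to arms, outcomes or the Go rule. The stated precision becomes less favourable.

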
### D. Approach

#### D.1 Preliminary Data

UE pilot study: Pilot data from patients with schizophrenia at the Nathan Kline Institute (NKI) and Rutgers show good retention with 6 of 7 patients (86%) completing at least 30 sessions. This is similar to previous single-site cognitive remediation studies and to an average retention rate of 87% in a metaanalysis of 40 cognitive remediation studies in schizophrenia. This also matches the 93% retention rate of UE studies in healthy young adults carried out by [name] (co-investigator and developer of UE). Preliminary data show UE is well tolerated, and even enjoyed, as described in our recent publication. Across participants, CS improved 32%, with an increase in the peak contrast spatial frequency of 1 cycle/degree (pre-training peak spatial frequency of  $3.14 \pm 0.24$  vs. post-training of  $4.15 \pm 0.70$ , p=.14, d=0.96). Additionally, patients improved on contour integration (p=.11, d=0.85). With such a small sample (N=6), our results were not statistically significant. However, the magnitude of CS improvement is similar to that from published studies of UE.

UE findings in non-psychiatric samples: In previous research on UE conducted by [name], CS improved in healthy normal-sighted individuals after  $\sim$ 30 sessions of training, with effect sizes ranging from

d=1.6 for LSF to 0.63 for HSF stimuli. In another study, college baseball players displayed significant improvements in CS (Fig. 1) and batting average $^{70}$ after UE training, with effect sizes ranging from d=0.34 to 0.59 (with the lowest effect size for CS to HSF stimuli). Additionally, university students demonstrated improved reading ability after UE training. Specifically, reading acuity improved an average of 13% (d=0.38), moving from a pre-training mean logMAR acuity of -0.06 to a post training value of -0.11, (SD=0.02). Reading speed improved 13% (d=0.57), moving from a pre-training mean value of 240.0 words/minute to a post-training value of 270.6 words/minute  $(SD=8.28)^{21}$ . In addition, older adults with presbyopia

displayed improved CS after undergoing UE training. It is important to note that in the studies of UE in which

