# **D.6.b Visual Targets**

Contrast Sensitivity: CS functions will be obtained by presenting 5 horizontal sine-wave gratings at the following SFs: 0.5, 1, 4, 7, and 21 cycles per degree. Spatial frequency is the number of pairs or cycles of light and dark bars in 1 degree of visual angle, expressed as cycles/degree, with fewer pairs corresponding to lower SF. Each grating will be presented for 32 milliseconds. An up-and-down transformed response method will be used to obtain contrast thresholds with a criterion of 70.7% correct responses for each SF. The mean of 10 reversals will be used to obtain thresholds. Presentation of the different SF gratings will be interleaved in a random order. A spatial 2-alternative forced-choice procedure will be used. Gratings will be presented on either the right or left side of the screen, and the participant's task is to determine on which side the gratings appeared. Results will be plotted as CS (which is the reciprocal of threshold) vs. SF. Increased CS indicates better performance. Participants will be tested binocularly after being light-adapted to the background luminance of the display for 15 minutes. Test re-test reliability of this measure in a group of 15 controls and 31 patients (tested at the [name] lab at NKI) was an ICC of .76 at 0.5 cpd and .67 and 1 cpd. The test-retest reliability is weaker at the peak SF of 4 cpd (.25) and improves with higher SFs (ICC=.69 for 7 cpd and .57 for 21 cpd). The target variable is the average CS for the two LSFs (0.5 cpd and 1 cpd). We expect to see more of an effect of the remediation on LSF, but we will also assess CS at the other SFs, and specifically compare LSF

results to results at 7 cpd, which also has high reliability, to determine if effects are LSF-specific. VEP Contrast Responses: This VEP technique was developed by [name] and colleagues and has been used in studies of schizophrenia , autism^82, and glaucoma detection. The response measures are quickly and easily obtained, requiring no behavioral response from the participant. Parameters to be used have been optimized in our studies of schizophrenia. Steady-state VEPs are elicited to checkerboard patterns that are luminance-modulated sinusoidally (~12 Hz) with contrast increases in 7 discrete octave steps. Each

ure 4: VEP Contrast stimuli examples				
4%	8%	16%	32%	64%

[figure not shown]

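### The pilot d=0.96 behind the R61 adequacy statement is an effect on peak spatial frequency; no patient pilot effect is reported for the psychophysical CS target

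*Combined protocol and SAP*

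**What the plan says.** D.1 Preliminary Data reports, for the UE pilot, "CS improved 32%, with an increase in the peak contrast spatial frequency of 1 cycle/degree". The parenthesis that follows gives peak spatial frequency before training (3.14 ± 0.24) and after it (4.15 ± 0.70), with p=.14 and d=0.96. The text adds "With such a small sample (N=6), our results were not statistically significant".

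D.3, in the rationale for the effect-size choice, cites the same pilot as "Even larger effect sizes were seen for changes in CS (d=0.96), and PO (d=0.85) in our small pilot sample of patients with schizophrenia". It discounts the figure for small size and lack of a control group, then lists it among the findings that make d=0.4 a conservative Go level.

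D.3, Sample size determination, says that 20 per group was chosen so that the 95% interval excludes zero when the true effect is 0.4. It gives that interval as .02 to .91, derived from the CS measure in the pilot, and continues: "Since the observed effect size in that pilot data was actually much larger, 0.96, we are confident that we will be adequately powered".

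D.6.b defines the psychophysical outcome: "The target variable is the average CS for the two LSFs (0.5 cpd and 1 cpd").

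**The concern.** One number carries two labels. Peak spatial frequency is the place on the frequency axis where the sensitivity curve is highest, in cycles/degree. CS is the reciprocal of the contrast threshold at a given frequency. The peak can move from about 3 to about 4 cycles/degree with no change in sensitivity at 0.5 and 1 cpd, so 0.96 is not evidence about the target variable.

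What is at stake is the statement that the R61 is adequately powered. It is argued directly from 0.96. Without that figure, no patient CS effect size stands behind it, and the remaining design value is d=0.4.

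**Working it through.** **1. Where 0.96 is attached.** In D.1 it closes the peak-spatial-frequency parenthesis, and no other pilot quantity is given that value. The CS gain of 32% has no SD, p-value or d of its own. Also, 4.15/3.14 = 1.32, so the 32% equals the relative rise in peak frequency. That may be coincidence, but it leaves open whether the pilot text holds any separate result on the size of CS. The other CS measure, the ssVEP, has no pilot training effect either.

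**2. Can 0.96 be reproduced from the printed figures?** The difference is 4.15 − 3.14 = 1.01.
- ± read as SD: 1.01/√((0.24² + 0.70²)/2) = 1.01/0.523 = 1.93.
- ± read as SE with n=6: 1.93/√6 = 0.79.
- Paired t-test with p=.14 and 5 df: t = 1.753, and 1.753/√6 = 0.72 in units of the SD of change.

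None gives 0.96. The ± values, the test and the standardiser are all undefined, so this shows only that the figure cannot be reproduced.

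**3. The stated interval for d=0.4.** The plan gives .02 to .91 (midpoint 0.465, half-width 0.445). For a between-group d with 20 vs 20:
- SE = √(1/20 + 1/20 + 0.4²/(2×40)) = √0.102 = 0.319.
- 0.4 ± 1.96 × 0.319 = -0.23 to 1.03; the noncentral-t interval is -0.23 to 1.02.

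Other layouts do not reproduce it: 40 vs 20 gives -0.14 to 0.94, 40 vs 40 gives -0.04 to 0.84, and one sample of 20 gives -0.06 to 0.85. If d were instead scaled by the raw-score SD with a pre-post correlation of 0.8 (assumed), the interval would be 0.4 ± 1.96 × √0.1 × √0.4 = 0.01 to 0.79, which does not match either.

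**4. Power at 20 per arm.** Assumptions: two-sided α = 0.05, two-sample t-test on change scores, d scaled by the SD of change, 38 df, noncentrality d√(20/2).

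| True d | Source of value | Noncentrality | Power |
|---|---|---|---|
| 0.40 | Go level and sample-size section | 1.26 | 23% |
| 0.45 | low end of the non-psychiatric low-frequency range, D.1 | 1.42 | 28% |
| 0.96 | pilot figure | 3.04 | 84% |

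The last row also treats a within-group pre-post d as a between-group d of change, which the pilot did not measure.

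**The case against.** The best defence is that 0.96 did no design work. The sample size was set on an interval at d=0.4, and 0.96 follows as reassurance. Relabelling it changes no sample size, threshold, endpoint or analysis. D.3 already says that the true effect is probably lower, and supports d=0.4 with cognitive remediation trials, auditory training (0.65 to 0.875), backward-masking training (0.43) and contour practice (phi=0.63). D.1 also reports UE effects on low-frequency CS directly, with average d from 0.45 to 1.0 across studies and 1.6 in one study.

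All of that stands as fact. It does not cure the problem. The discount in D.3 concerns sample size and the missing control group; it does not disclose that a different variable was measured, and the sample-size section carries no such caveat. The low-frequency effects come from non-psychiatric samples and are described for the trained group.

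A reader might also infer more than the documents support:
- **That 0.96 contradicts its own p-value.** This assumes d is change divided by the SD of change. With a raw-score SD, 0.96/√(2(1 − r)) = 0.72 at r of about 0.10, so p=.14 and d=0.96 are compatible.
- **That the retest ICC of .25 at 4 cpd undermines the pilot figure.** That ICC is for CS at a fixed frequency, not for the location of the peak.
- **That low-frequency CS decides the Go.** D.3 Milestones accepts either CS task or either PO task.
- **That the plan has no effect-size basis at all for its target.** It has one, but not from patients.

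**Conclusion.** The point holds as a mislabelled input and an unsupported adequacy statement. D.3 twice presents a peak-spatial-frequency effect as a CS effect, and the sample-size section rests its confidence on it. No patient pilot effect size for mean CS at 0.5 and 1 cpd appears in the documents. At 20 per arm, power is about 84% if 0.96 is taken as the true between-group effect, but 23% at 0.4, and the interval at d=0.4 runs from about -0.23 to 1.02 rather than .02 to .91.

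These figures assume a two-sided 0.05 t-test and d scaled by the SD of change scores, which is the natural reading of D.3 Milestones. The power figures describe tests of significance. They are not the chance of a Go, which depends on the observed d reaching 0.4. It does not follow that the R61 must be redesigned or that d=0.4 is the wrong Go level.

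**What to change.** 1. In both D.3 places, relabel 0.96 as an uncontrolled pre-post effect on peak spatial frequency in six patients, and define its standardiser and the ± values.
2. Delete the adequacy statement. State instead what 20 per arm delivers: about 23% power at d=0.4, 28% at 0.45 and 84% at 0.96, with the assumptions given.
3. Report the pilot effect on mean CS at 0.5 and 1 cpd with its interval, if those frequencies were recorded. The documents do not show that they were. Otherwise, state that none is available and cite the D.1 range of 0.45 to 1.0 as non-psychiatric.
4. Replace .02 to .91 with an interval for a between-group d of 0.4 at 20 vs 20 (about -0.23 to 1.02), and revise the sentence saying that the sample size ensures an interval that excludes zero.

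The cost is a few sentences and, if the data exist, a small re-analysis of six patients. The justification becomes less favourable.
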